### **Protocol Deviations**

Protocol deviations represent incidents, circumstances, or processes that occur during the research protocol that are not part of or are inconsistent with the approved IRB protocol, with the policies and procedures outlined in this manual, or with the Federal regulations. For example, if a participant does not fill out a consent form prior to participation in the study, protocol has been violated. Investigators are required to follow the IRB approved protocol. Once the PI or any member of the study team identifies an instance where the approved protocol has been seriously altered this must be promptly reported to the CRC IRB within 5 days. Minor changes, such as study visits/procedures that are either omitted, conducted outside of the visit window, or in a different order than specified in the protocol that do NOT affect or have the potential to affect subject safety or data integrity, should be submitted within 20 working days of the incident. A Deviation Report form must be submitted to the CRC IRB for review. The submitted form and the IRB's response is kept in the Protocol Deviations Submissions folder in Dropbox

Protocol deviations are reviewed by a member of the IRB staff. PIs are required to provide the IRB with CAPs (corrective action plans) for all deviations which explain how the PI will prevent the deviation from recurring. The IRB may approve, request modifications to, or disapprove CAPs. Frequent or serious protocol deviations can cause the IRB to institute an audit of a research protocol and referral to the appropriate institutional research oversight committee. A listing of all protocol deviations is available to the board at the end of each annual progress report. The board uses the information in the protocol deviations report and the Corrective Action Plan (CAP) in making its determination as to whether continuation of the research is appropriate.

## Unanticipated Problems and Adverse Events.

The CRC IRB requires that any unanticipated problem be reported using the Adverse Events found on the shared drive. The following information defines what unanticipated problems are and explains how to manage them:

Upon submitting an Adverse Events form to the CRC IRB and receiving a response letter, an update to the binder list stating the date of the correspondence should be

the RA. Copies of the submitted form and the response letter are also kept

## **Reporting Unanticipated Problems to the IRB**

Effective immediately, BU/BMC investigators will no longer individually report all SAEs to the IRB. Instead, only those events that meet **all three** of the following criteria: 1) is unexpected (in terms of nature, severity, or frequency) given (a) the research procedures that are described in the protocol-related documents (such as the IRB-approved research protocol and informed consent

document), and (b) the characteristics of the subject population being studied; AND 2) is related or possibly related to participation in the research (in this guidance document, *possibly related* means there is a reasonable possibility that the incident, experience, or outcome may have been caused by the procedures involved in the research); AND 3) suggests that the research places subjects or others at a greater risk of harm (including physical, psychological, economic, or social harm) than was previously known or recognized, OR are by definition SERIOUS (Note: all incidents, experiences, or outcomes that are unexpected AND related or possibly related AND are SERIOUS are automatically unanticipated problems). Based on the above definition, many (if not most) AEs and SAEs that are currently reported to IRBs are NOT by definition *unanticipated problems* and, therefore, do NOT--according to the regulations--have to be reported to the IRB.

The "Unanticipated Problems and Summary of Events Report" (UPSER) should be used to report all events that meet the definition of *unanticipated problems* to the IRB. The UPSER may be submitted by any member of the study staff at any time, even when an amendment or progress report is pending. These *unanticipated problems*, whether they are internal or external, must be reported to the IRB within two business days of the investigators learning of the event. Internal events are those experienced by subjects enrolled by BU/BMC investigators no matter where the "event" occurs. For single site studies, all events are internal events. Only those internal events that meet the definition of *unanticipated problems* need to be individually reported to the BU/BMC IRB.

External events are those that occur to subjects enrolled at other (non-BU/BMC) sites. Investigators in multi-center trials receive SAE reports of all external SAEs from all sites. These external SAEs no longer have to be routinely reported to the BU/BMC IRB on individual SAE reports. Instead, external SAEs will ideally be reviewed by a monitoring entity (e.g., the research sponsor, a coordinating or statistical center, a DSMB/DMC, an AE monitoring committee) or the investigators, in accordance with a monitoring plan described in the IRB-approved protocol. These entities should make the determination as to whether the SAE represents an *unanticipated problem*. Instances when external SAEs are determined to be *unanticipated problems* should be rare; when they occur, they must be submitted to the IRB. The submission must include an explanation from the investigator or sponsor as to why the event is considered an *unanticipated problem*, and a description of the proposed protocol changes or other corrective actions to be taken [Note: Problems that are unexpected, related, or possibly related and represent a greater risk to subjects will almost always require modification to the protocol and consent].

#### **Managing IRB Content**

The RAs are primarily responsible for managing content related to the IRB and for informing the study team of submission/revision deadlines. The RAs will construct necessary IRB documents and provide them to Drs. [name] or [name] for review before submission. Copies of all IRB correspondence sent or received to the PD or PI should be given to the RA so these documents can be filed in the IRB folder

The IRB **Consists** of a folder for each amendment submission, an Adverse Events folder, Approved Documents folder, Protocol Deviation Submissions folder, and Continuing Review folder. Each Amendment folder is titled with the date it was submitted, the amendment number, and the approval status (i.e., submitted, approved, rejected, in-progress). In each amendment folder, is the Amendment form, the approval letter/IRB response letter, and the submission materials.

### Adverse event management and report

# Definitions

OHRP guidance on unanticipated problems and adverse events: https://www.hhs.gov/ohrp/sites/default/files/ohrp/policy/advevntguid.pdf

Guidelines and FAQs: http://www.bu.edu/researchsupport/compliance/human-subjects/

# Adverse Event (AE)

AE is defined at this institution as, "any untoward or unfavorable medical occurrence in a human subject, including any abnormal sign (for example, abnormal physical exam or laboratory finding), symptom, or disease, temporally associated with the subject's participation in the research, whether or not considered related to the subject's participation in the research."

## Serious Adverse Event (SAE)

SAE is defined at this institution as, any adverse event that:

- 1. results in death;
- 2. is life-threatening (places the subject at immediate risk of death from the event as it occurred);
- 3. results in in participant's hospitalization or prolongation of existing hospitalization;
- 4. results in a persistent or significant disability/incapacity;
- 5. results in a congenital anomaly/birth defect; or
- 6. based upon appropriate medical judgment, may jeopardize the subject's health and may require medical or surgical intervention to prevent one of the other outcomes listed in this definition (examples of such events include allergic bronchospasm requiring intensive treatment in the emergency room or at home, blood dyscrasias or convulsions that do not result in hospitalization).

## **Unexpected Adverse Event**

Definition: Any adverse event occurring in one or more subjects participating in a research protocol, the nature, severity, or frequency of which is not consistent with either: 1) the known or foreseeable risk of adverse events associated with the procedures involved in the

research that are described in (a) the protocol related documents, such as the IRB approved protocol, any applicable investigator brochure, and the current IRB approved informed consent document, and (b) other relevant sources of information, such as product labeling and package inserts, or 2) the expected natural progression of any underling disease, disorder, or condition of the subject(s) experiencing the adverse event and the subject's predisposing risk factor profile for the adverse event.

### Adverse event tracking

All Adverse events submissions and IRB responses to the submission should be saved in the BU Dropbox folder: Dropbox (BOSTON UNIVERSITY)/UP-AUD/IRB/Adverse Events. When adverse events come up throughout the course of the study they should be logged in The Adverse Event Tracking Log in Google Sheets. Here is the link:

https://docs.google.com/spreadsheets/d/1CdxXESTvWHNcWOqDNgfScTMzdvnbhdAo6aKv72 9VK-o/edit#gid=0

This link is shared with the [contact] account.

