## **General Contact Information**

# **Staff Personnel Contacts and Locations**

# **Research Design**

In this clinical trial, research personnel will further assess the UP's effectiveness in reducing alcohol consumption in participants with comorbid AUD/AXD. Participants will be randomized to one of two conditions: 1) treatment with the UP or 2) treatment with therapist-guided *Take Control* (TC; a psychoeducation-based, alcohol reduction program developed by NIAAA). In addition, a subset of twenty-five participants (UP condition only) will complete functional magnetic resonance scanning (fMRI) to examine the effects of the UP on changes in

brain activity in areas important to regulation of emotional and reward processes implicated in excessive alcohol consumption.

The primary hypotheses are that the UP compared to TC will: 1) be superior in acute symptom reduction from pre- to post-treatment, and 2) evidence greater reductions in percent days heavy drinking, percent days of drinking per week, and alcohol craving.

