# Table 1. Visit Projection Table

#### **Subjects**

A total of 60 participants will be enrolled, with a target male to female ratio of 33:27. This ratio reflects the higher prevalence rates of AUDs in biological men compared to biological women. Forty participants will be randomized to the UP condition and 20 to the Take Control condition. In addition, 25 participants from the UP group will receive two fMRI scans (pre- and post-treatment).

Participants will be recruited via flyers, brochures, lab website and StAR Facebook page, MBTA advertisements, etc. Telephone screenings will determine initial eligibility, and potential research participants will be invited to CARD, located at Boston University, for a more extensive assessment of alcohol use and emotional disorders.

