# After the Scans:

- Go into the scanner room and help the participant out of the scanner bed. Ask him/her to sit and stand up slowly, as he/she may be dizzy or weak after lying still in the scanner for an extended period of time
- The participant can then change back into street clothes and is free to leave
- Strip the linens off the scanner bed and put them in the hamper along with the participant's used scrubs
- Make a copy of the participant's screening form, give the original to the technician, bring the copy back to CARD, and file in participant's binder

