# Monitoring of Safety Data by the DSMB

- 1. Unblinded Reporting Safety information for this study will be reported to the DSMB in an unblinded manner. A statistical penalty will not be assessed for the ongoing unblinded review of safety by the DSMB.
- Range of Safety Reporting to the DSMB It is considered necessary for the purpose of monitoring the safety of the study that the DSMB review not only adverse events (AEs) and serious adverse events (SAEs), but also other data that may reflect

differences in safety between treatment groups. This includes treatment retention rates and reasons for dropout.

- 3. Serious Adverse Events Expedited review will occur for all events meeting the FDA definition of Serious Adverse Events (SAEs) i.e., any fatal event, immediately life-threatening event, permanently or substantially disabling event, an event requiring or prolonging hospitalization, or any congenital anomaly. Included is any event that a study investigator or the DSMB judges to impose a significant hazard, contraindication, side effect, or precaution. All relevant information will be reported to the DSMB for each SAE, including information about the event and its outcome, and the subject's medical history and current conditions. If the SAE is considered an unanticipated problem (for more information see the above section on Unanticipated Problems) then reporting to local IRBs will be completed within 2 business days of the unanticipated problem. Notification by e-mail shall be made to the DSMB within 7 days of the occurrence of any SAE.
- 4. Non-Serious Adverse Events At yearly intervals during the course of the study, as indicated by the grant and in accordance with the CRC IRB, and then again at its completion, the DSMB will be provided with unblinded summaries of the numbers and rates of adverse events by treatment group. These reports will include types of events, severity, and treatment phase. Data on individual non-serious adverse events is not expected to be needed for this review.
- 5. Other Safety-Related Reports At yearly intervals throughout the course of the study, the DSMB will also receive unblinded summary reports of treatment retention and reasons for dropout, by treatment arm and study phase.

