## **Data Safety Monitoring Plan**

Because all BU CILSE procedures are nonsignificant risk in nature, the co-investigator at BU CILSE will execute a Data Safety Monitoring Plan (DSMP) covering BU CILSE procedures.
This DSMP includes monitoring and regular reporting of accumulated study data to Drs. [name] and [name]. DSMP procedures covering subject safety will be executed if necessary to protect the safety of human subjects. Subject safety and adverse events will be monitored and assessed by study staff during each study visit. If any adverse events should occur, the subject can withdraw voluntarily or, if a contraindication to fMRI scans or other disqualification from study eligibility becomes apparent, at the discretion of the BU CILSE co-investigator.

Adverse events related to BU CILSE study procedures will be reported to [name]. Serious adverse events, non-serious unexpected adverse events that are related or possibly related to the study, and unanticipated problems involving subjects or others will be reported to [name] as soon as possible and within 5 working days/7 calendar days. Within 10 working days of this notification, a full written report regarding events will be submitted to [name]. Events that do not fall into the above categories will be reported to [name] in summary format for inclusion into the annual IRB continuing review report.

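### Outside imaging, adverse-event capture is passive, and the plan does not say whether events from UP-only imaging enter the DSMB's by-arm rates

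*Combined protocol and SAP*

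**What the plan says.** All references are to the combined protocol and SAP.

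- *Adverse event tracking*: "When adverse events come up throughout the course of the study they should be logged in The Adverse Event Tracking Log in Google Sheets". No question, form, visit or responsible role is attached to this.
- *Assessment Measures Administration*: the schedule has no adverse-event row.
- *Data Safety Monitoring Plan*: the imaging-centre co-investigator "will execute a Data Safety Monitoring Plan (DSMP) covering BU CILSE procedures". Within that plan, "Subject safety and adverse events will be monitored and assessed by study staff during each study visit". Serious events, unexpected related events and unanticipated problems go to a named recipient within days. The remainder are passed on "in summary format for inclusion into the annual IRB continuing review report". The DSMB is not mentioned.
- *Research Design*, *Subjects* and *Treatment Conditions and Specifications*: 25 of the 40 UP participants have two scans each, one between randomisation and session 1 and one within two weeks after the last session. None of the 20 TC participants is scanned.
- *Monitoring of Safety Data by the DSMB*, item 4: each year and at completion the board gets "unblinded summaries of the numbers and rates of adverse events by treatment group", with event type, severity and treatment phase. Individual data on non-serious events are not expected to be needed.
- *Adverse Event (AE)*: the definition covers any untoward medical occurrence, related or not.
- The scanning instructions foresee possible claustrophobia and peripheral nerve stimulation. *After the Scans* has the participant rise slowly "as he/she may be dizzy or weak after lying still in the scanner for an extended period of time".

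**The concern.** A by-arm safety table is readable only if events are sought in the same way in both arms, and if procedures outside the comparison are kept apart from it. Here the general rule waits for events to surface. The one stated per-visit check belongs to a procedure given in one arm only, and that procedure can itself cause minor events that meet the adverse-event definition.

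At stake is the DSMB's yearly reading of non-serious events. It could see a UP excess that belongs to the scanner and not to the psychotherapy, or it could be shown a table from which routine imaging events are absent without knowing it. Waiting for reports also tends to leave the record thin, which matters most in the 20-person TC arm.

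**Working it through.** The plan states no adverse-event rate, capture rate or related calculation, so there is no figure to reproduce. The check is a reading of the text followed by illustrations on stated assumptions.

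**1. Does another section supply a general enquiry?** In both arms the manual has breath alcohol, drinking recall and the ODSIS/OASIS at each session; laboratory tests and vital signs at screening and last session; a triggered withdrawal scale; and a form on changes in medication, treatment or lifestyle. Events may surface through these, but none asks generally about adverse events.

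**2. Where do routine imaging events go?** The text allows two cases.

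- *They enter the by-arm table.* UP then carries events from a procedure that TC does not receive.
- *They do not.* The imaging plan then offers only the annual IRB report, and the DSMB has no stated route to them.

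Serious events are different: item 3 of the DSMB section gives the board expedited review of all of them. The gap concerns non-serious events.

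**3. Illustration, first case only: events caused by scanning.** Assume background risk b = 0.20 in both arms and a loggable scan event in a fraction q of the 25 scanned participants. Neither figure is in the documents.

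UP proportion = [25(b + (1 - b)q) + 15b] / 40

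- q = 0.1: (25 × 0.28 + 3) / 40 = 10/40 = 25%
- q = 0.2: (25 × 0.36 + 3) / 40 = 12/40 = 30%
- q = 0.3: (25 × 0.44 + 3) / 40 = 14/40 = 35%

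TC stays at 20%, so the gap is 5 to 15 points. In the second case this contribution is zero.

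**4. Illustration: unequal capture at equal true risk.** This is a separate mechanism. Let s be the chance that an event is recorded when it must surface unprompted, and e the chance when it is assessed at imaging visits. Both are assumed.

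Recorded UP:TC ratio = (15s + 25e) / (40s)

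| s | e | Ratio |
|---|---|---|
| 0.3 | 0.6 | 19.5/12 = 1.63 |
| 0.5 | 0.8 | 27.5/20 = 1.38 |
| 0.7 | 0.9 | 33/28 = 1.18 |
| 0.9 | 0.95 | 37.25/36 = 1.03 (1.035 before rounding) |

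These lean high, because they apply e to every event in a scanned participant, although there are only two imaging visits.

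**5. Illustration: under-recording.** If true risk in TC is 20-30% and half of events surface unprompted, 20 × 0.2 × 0.5 = 2 to 20 × 0.3 × 0.5 = 3 participants are recorded, where 4 to 6 had an event. At 20% true risk the chance that none is recorded is (1 - 0.10)^20 = 0.12. The same loss applies to UP participants wherever capture is passive.

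**6. What equal questioning leaves behind.** UP has 16 sessions over 16-21 weeks and TC has 12 over 12-16 weeks. At an equal weekly event rate, the treatment-period count per participant is still 16/12 = 1.33 to 21/16 = 1.31 times higher in UP. With two follow-ups, a question at every contact is asked 18 times in UP and 14 in TC. Item 4 gives no denominator for its rates.

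**The case against.** **Routing is not shown.** The imaging plan sends routine events to the IRB report. Taken literally, they never reach the by-arm table and the illustrated gap vanishes. This stands: the inflation is conditional.

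**No contradiction.** A reader might infer that the imaging plan and the DSMB section disagree. They do not. The imaging plan is silent on the DSMB, its recipients' names are removed from the public text, and the DSMB section makes no exception for imaging. Silence leaves a question open; it is not a conflict.

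**Phase reporting already helps.** Scan 1 precedes session 1, so tabulation by phase separates its events from therapy, provided that a pre-treatment phase is among those shown. The ambiguity that remains is mainly at scan 2.

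**Scan events may be rare.** Claustrophobia and MRI contraindications are exclusions, nerve stimulation is called a small possibility, and the dizziness remark is a precaution. The 10-30% range has no support in the documents.

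**The per-visit sentence could be read more widely.** It might mean all trial visits. Its setting limits it to imaging procedures, and no therapy section repeats it. Even on the wider reading, nothing supplies a question or a role.

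**Consequences are limited.** No study aim tests safety by arm, stopping is at the board's discretion, and serious events are reviewed individually. Even 4 to 6 affected TC participants would support only a weak comparison. All of this stands, and it makes the point a low-cost improvement. The validity of the efficacy aims is not in question.

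**Conclusion.** The point holds in a limited form. Outside imaging, the manual states only passive capture. The sole per-visit assessment belongs to a procedure confined to UP, and the documents leave open whether imaging events are counted in the by-arm rates. Each answer has a cost: an arm comparison mixed with scanner events, or routine imaging events without a stated path to the DSMB. Passive capture may lower the recorded count in both arms.

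The size is unknown. The 5-15 point gap and the ratios of about 1.03 to 1.63 rest on assumed event and capture rates, and the first applies only if scan events are tabulated by arm. A reader might infer that the DSMB's rates will be biased against UP, or that TC participants go unmonitored. The documents support neither: the routing is unstated, and both arms have structured measures through which events can surface.

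**What to change.** - *Adverse event tracking*: have the research assistant ask one fixed, open adverse-event question at each existing session and follow-up contact in both arms, in person or remotely. Record the onset date and whether the event arose at a scan visit. The tracking log is not in the public document, so these columns may already exist.
- *Monitoring of Safety Data by the DSMB*, item 4: compare UP with TC without scan-visit events, using person-time rates or a common window such as the first 12 weeks, because the arms differ in treatment length and number of contacts. Show scan-visit events on a separate line with scanned participants as the denominator.
- *Data Safety Monitoring Plan*: state whether the per-visit assessment covers therapy visits, and copy the imaging event summary to the DSMB.

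The cost is slightly more research-assistant time, at most two log columns, one table line and a second addressee for an existing summary. More minor events will be recorded.
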